### 6.1. Treatment Administration

The following treatments will be administered:

Product	Supplied as:
MNK6106	1 g immediate release (IR) MNK6106 tablet
Rifaximin	550 mg tablet

MNK6106 tablets, 1 g, are supplied as white, film coated immediate release tablets for oral administration. Each tablet contains 1 g of L-Ornithine phenylacetate. The inactive ingredients include [REDACTED]

Rifaximin tablets, 550 mg, are supplied as a pink-colored, oval, biconvex tablet with "rfx" debossed on 1 side and plain on the other.

**Table 2: Summary of Treatment Groups, Frequency and Dose**

Treatment	Frequency	Dose	Total Daily Dose	Total Dose (5 days)
MNK6106	tid	2 g	6 g	30 g
MNK6106	bid	4 g	8 g	40 g
MNK6106	tid	4 g	12 g	60 g
Rifaximin	bid	550 mg	1.1 g	5.5 g

Note: bid = twice daily; tid = 3 times daily.

For the 3 times daily dosing regimen, the doses will be given at 8 AM, 1 PM, and 6 PM ( $\pm 60$  minutes); for twice daily dosing, the doses will be given at 8 AM and 6 PM ( $\pm 60$  minutes). Each dose will be administered with an 8 oz glass of room temperature water, and the subject will be required to swallow the tablet whole without chewing or crushing it, and to drink all the water. The date and actual (clock) time that the subject receives the MNK6106 study drug and the dose amount administered will be recorded on the electronic case report form (eCRF). Any

---

deviations from the dosing schedule and instructions described in this protocol will also be recorded. Each subject will be closely supervised for ingesting each of the doses and the required amount of water. The entire dose must be administered within 15 minutes.

Any loss of the study drugs will be documented and reported to Mallinckrodt Clinical Supply Management, with the approximate amount lost estimated and recorded. Replacements will be made accordingly.

The study drugs will be administered under fed (30 minutes after start of meal) conditions. Lunch and dinner will be served at approximately 30 minutes prior to dosing.

After each dose, the subjects will be required to remain in an upright position for at least 2 hours after dosing. In addition, subjects will also be required to refrain from anything more than light exercise while confined at the study site.

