**Table 1: Schedule of Study Events (Continued)**

Assessment/Procedure	Screening	Begin Confinement (Day -1)	Treatment Period (Days)					End Confinement (Day 6)	Final Visit (7 days post-dosing) (+ 3 day a window)
			1	2	3	4	5/ET		
Week			1						2
Day	-28 to -1	-1	1	2	3	4	5/ET	6b	12
Study Visit Number	1		2	3	4	5	6		7
Laboratories: hepatitis and human immunodeficiency virus (HIV) serology j	X								
Serum pregnancy test/FSH k	X								X
Urine pregnancy test l		X							
Concomitant medications/therapies	X	X	X	X	X	X	X	X	X
Adverse events m	X	X	X	X	X	X	X	X	X
Study drug dosing n			X	X	X	X	X		
Subject confinement		X	X	X	X	X	X		

ET = end of treatment; FSH = follicle stimulating hormone; ORN = Ornithine; PAA = Phenylacetate; PAGN = Phenylacetylglutamine; PD = pharmacodynamics; PK = pharmacokinetics.

a If circumstances occur such that this visit cannot occur within the specified window, the visit window may be extended to 14 days, after discussion with the sponsor.

b Subjects may be discharged from the clinic after the final PK samples are obtained. Subjects will be instructed to return for the final visit (7 days [+ 3 day window] after the last dose is administered).

c Height at screening only.

d Blood pressure, respiratory rate, pulse rate, and body temperature.

- 
- e ECGs on Days 1, 3, and 5/ET should be recorded one hour after last dose ( $\pm$  15 minutes). Complete ECG prior to PK sample collection if the timing is the same. Subject needs to be supine for greater than 10 min prior to ECG.
- f Samples for plasma AMM levels will be drawn at screening and on Days 1, 3 and 5/ET, predose in the morning immediately before breakfast and 4 hours ( $\pm$  15 minutes) after the morning dose, as well as at the final visit.
- g Samples for plasma PAA, ORN and PAGN will be drawn prior to the first dose on Day 1 (within 15 minutes prior to morning dose) and then prior to (within 10 min) and 1 hour ( $\pm$  15 minutes) after the last dose on Days 1, 3, and 5/ET.

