### 8.3. Treatment Period (Week 1; Day 1 to Day 5/ET) and Day 6 (Discharge)

After randomization, subjects will enter the study, and receive active treatment (1 of 3 MNK6106 dose regimens or rifaximin) for 5 days. Subjects will be confined to the study center overnight during the treatment period and discharged on Day 6. The following procedures will be carried out on Days 1, 2, 3, 4 and 5 unless otherwise stated:

- Perform a limited physical examination (Day 1 only).
- Record the subject's weight and waist circumference (Day 1 and Day 6 only).
- Record the subject's vital signs (Day 1 through Day 6).
- Record ECG (Days 1, 3 and 5/ET only) at 1 hour after the last dose ( $\pm$  15 minutes). Complete the ECG prior to the PK sample collection if the timing is the same.
- Collect blood samples for plasma AMM (to be drawn on Days 1, 3 and 5/ET only, predose in the morning immediately before breakfast and 4 hours ( $\pm$  15 minutes) after the morning dose), as well as on the day of the final visit.
- Collect a blood sample for plasma PAA, ORN and PAGN (to be drawn on Days 1, 3 and 5/ET only). A baseline sample will be drawn prior to the first dose on Day 1 (within 15 minutes prior to the morning dose) and then prior to (with 10 minutes) and 1 hour ( $\pm$  15 minutes) after the last dose on Days 1, 3, and 5/ET.
- Collect a urine sample for PAGN. For each 24-hour collection following the first dose of the day, all urine will be collected during the specified intervals, with the last collection for Day 5/ET being collected on Day 6. A baseline urine sample will also be collected predose on Day 1.
- Collect samples for chemistry, hematology, (Days 1 through 6) and urinalysis (Days 1 through 5 only).
- Record the Conn, MELD, HESA and C-P scores (Days 1 through 6).
- Perform study drug dosing.
- Record all concomitant medications/therapies (Days 1 through 6).
- Record and assess AEs/SAEs, including AESI (Days 1 through 6).

On the Day 6 visit (discharge):

If no clinical or laboratory abnormalities are observed, subjects will be discharged from the study on the morning of Day 6. The 24-hour urine collection for PAGN will be completed on Day 6 at the end of confinement.

Additional follow-up visits will be scheduled if a subject shows any clinical or laboratory abnormalities at this visit, as deemed appropriate by the investigator/designee (classified as unscheduled visits).

---

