#### **8.6.2. Electrocardiogram**

A 12-lead ECG will be obtained at screening and on Days 1, 3 and 5/ET at 1 hour after the last dose ( $\pm$  15 minutes). Complete the ECG prior to PK sample collection if the timing is the same.

---

Subject needs to be supine for greater than 10 minutes prior to ECG. The investigator (or investigator's designee who is a physician) will interpret the ECG and will record a global interpretation of the ECG (ie, "Normal" or "Abnormal") on the tracing.

Each ECG tracing must also include the signature of the investigator and the date that the ECG was interpreted. If the global interpretation is abnormal, the investigator will indicate on the tracing whether the abnormality is clinically significant or not clinically significant. A copy of each ECG and the physician's assessment will be filed with the source documents.

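### No scheduled on-treatment ECG can meet both the 2-hour upright rule after dosing and the supine-rest rule 1 hour after dosing

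*Combined protocol and SAP*

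**What the plan says.** **Posture after dosing.** Section 6.1, in the text following Table 2: "After each dose, the subjects will be required to remain in an upright position for at least 2 hours after dosing". The rule covers every dose and so all four arms. The same section says of dose intake: "The entire dose must be administered within 15 minutes".

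**ECG timing.** Three places agree on 1 hour after the last dose, each with a 15-minute tolerance either way:
- Section 8.6.2: "A 12-lead ECG will be obtained at screening and on Days 1, 3 and 5/ET at 1 hour after the last dose".
- Section 8.3: "Record ECG (Days 1, 3 and 5/ET only) at 1 hour after the last dose".
- Table 1 footnote e: "ECGs on Days 1, 3, and 5/ET should be recorded one hour after last dose". In the table the footnote mark sits only on Day 1, but its text names all three days.

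**ECG posture.** Section 8.6.2: "Subject needs to be supine for greater than 10 minutes prior to ECG". Table 1 footnote e has the same rule: "Subject needs to be supine for greater than 10 min prior to ECG". Section 8.3 repeats the timing but is silent on posture.

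**Use of the ECGs.** Under Section 8.6.2 the investigator or a physician designee reads each tracing as normal or abnormal and, if abnormal, marks its clinical significance. Under Section 7.1 a clinically significant cardiac finding after treatment starts, with QTcF change from baseline as one example, leads to a case-by-case judgement on whether the subject can continue.

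**The concern.** Both posture instructions are worded as requirements. They ask for opposite body positions over the same stretch of time after a dose. No section gives an exception for ECGs or says which rule takes precedence.

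A site could lie the subject down on time and depart from Section 6.1. It could keep the subject upright and depart from the supine rule. Or it could wait until the upright period ends and miss the ECG window. Section 10.1.1 does not let investigators change the plan on their own, except for an immediate hazard. Section 6.1 requires departures from the dosing instructions to be recorded.

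Two things are at stake. The first is a protocol departure built into every scheduled on-treatment ECG. The second is whether tracings are comparable within a subject. Screening is the only scheduled ECG before dosing, and the supine instruction of Section 8.6.2 covers it too. An on-treatment tracing taken in another posture or at another time would be a less clean comparison for the Section 7.1 judgement.

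**Working it through.** The plan gives no figure of its own to reproduce. The check compares intervals on the clock after a dose.

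**Inputs**
- Upright period: 0 to at least 120 minutes after each dose (Section 6.1).
- ECG time: 60 ± 15 minutes after the last dose (Sections 8.3 and 8.6.2, Table 1 footnote e).
- Supine rest: more than 10 minutes before the ECG (Section 8.6.2, Table 1 footnote e).
- Dose intake: up to 15 minutes (Section 6.1), used only as a sensitivity check.
- Scheduled on-treatment ECGs: 3 per subject (Days 1, 3 and 5/ET).
- Planned subjects: 48 (Section 9.1).

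**Main check**
1. ECG window: 60 − 15 = 45 minutes to 60 + 15 = 75 minutes.
2. Supine rest must begin before 45 − 10 = 35 minutes for the earliest ECG, and before 75 − 10 = 65 minutes for the latest.
3. Gap from the latest allowed ECG to the end of the upright period: 120 − 75 = 45 minutes.
4. Gap from the latest supine start to the end of the upright period: 120 − 65 = 55 minutes.
5. The ECG window and the rest before it therefore lie wholly inside the upright period.
6. Earliest ECG that respects both posture rules: later than 120 + 10 = 130 minutes. That is at least 130 − 75 = 55 minutes after the window closes.

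**Sensitivity to the dosing clock.** The most favourable reading starts the upright period when dosing begins and the ECG clock when dosing ends, 15 minutes later.
- Latest ECG: 75 + 15 = 90 minutes, still 120 − 90 = 30 minutes inside the upright period.
- Latest supine start: 80 minutes, still 120 − 80 = 40 minutes inside.

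The conflict remains.

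**Sensitivity to wording.** It makes no difference whether the last dose means the last of the day or the most recent one, or whether dosing is twice or three times daily, because the upright rule follows every dose. The supine text literally governs the minutes before the ECG. Those minutes alone break the upright rule, whatever the posture during the tracing.

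**Extent.** 3 × 48 = 144 tracings if 48 subjects are randomized and all complete treatment.

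**The case against.** The strongest reply accepts the clash but says it matters little. The supine requirement appears in two places and belongs to the specific ECG instruction, while the upright rule is one general sentence in the dosing section. A site following the ECG section would lie the subject down on time, and the tracings would then be comparable with one another. This is plausible and limits the likely harm. It does not remove the contradiction, since nothing tells a site that the ECG text prevails.

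Several stronger inferences are tempting, and the documents do not support them:

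- *That heart-rate or QTcF results would mix drug effect with posture.* No summary of either is specified. Section 9.5.1 describes adverse-event summaries, and the safety endpoints in Section 3.2 are AEs and SAEs. QTcF otherwise appears as a screening exclusion and in the individual judgement of Section 7.1.
- *That sites will resolve the conflict differently.* They could, but nothing in the text shows that they will.
- *That a late ECG would break an ECG–PAA analysis.* The ECG and the PK sample share a nominal time, and the protocol sets their order: "Complete the ECG prior to the PK sample collection if the timing is the same". No ECG–concentration analysis is named. The specified PAA safety relationship is with neurotoxicity.
- *That every planned ECG is affected, 144 of 144.* The screening ECG precedes dosing and is unaffected. The 144 is a planned maximum: Section 4.1 says approximately 48 subjects, and Section 9.1 does not replace those who discontinue.
- *That body position and time are not recorded.* The eCRF pages are not among the documents, so a missing field cannot be asserted. Lying down early is also arguably a recordable departure already under Section 6.1.

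**Conclusion.** The point holds as an internal inconsistency. Followed literally, Section 6.1 and the ECG instructions cannot both be met at any scheduled on-treatment ECG: 3 of 3 per subject, in all four arms. The shortfall is too wide for the stated tolerances to absorb, and allowing the full dose-intake time does not close it.

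The consequence is narrow. It consists of departures that sites cannot avoid, and possible inconsistency in the posture or timing of tracings that inform individual continuation decisions. It does not extend to the ammonia endpoint or to any specified analysis.

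The conclusion rests on reading both posture instructions as binding and on the absence of any stated exception. Manuals outside these documents might contain one, but the protocol refers to none on this point. The review takes no position on which rule should give way.

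**What to change.** Reconcile Section 6.1 with Sections 8.3 and 8.6.2 and Table 1 footnote e, so that a single instruction covers posture and timing for the Day 1, 3 and 5/ET ECGs in all arms. One of the rules needs a stated exception, and the sponsor should decide which. If the eCRF does not already capture body position and clock time at each ECG, record them, so that tracings made under the conflicting text can be identified.

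The cost is a short wording change and at most a small eCRF addition, with no extra visit or procedure. Because Section 10.1.1 requires an amendment for any change in the study plan, the wording would go through a protocol amendment with IRB/IEC approval.

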## **6.2. Study Treatment Preparation/Handling/Storage/Accountability**

MNK6106 tablets are packed into high-density polyethylene bottles with child-resistant caps, 60 tablets per bottle.

The bottles of MNK6106 and rifaximin should be stored at room temperature 20°C to 25°C (68°F to 77°F); excursions are permitted between 15°C to 30°C (59°F to 86°F).

The sponsor will supply MNK6106 and rifaximin. The investigator or investigator's designee will maintain the following records: receipt of shipments, dispensation to subjects, and return of empty, partially used, and unopened bottles. Reasons for departure from the expected dispensing regimen must also be recorded.

Study drug should not be returned before the designated study monitor has checked the drug accountability records with the study site personnel after database lock.

Upon receipt of the study drug supplies, the investigator or investigator's designee will conduct an inventory, follow the process for acknowledging receipt of the study drug, and complete appropriate form(s). One copy of the receipt and the packing slip must be retained.

At the completion of the study, to satisfy regulatory requirements regarding drug accountability, all study treatments will be reconciled and retained or destroyed according to applicable regulations.

The investigator or designee will confirm that appropriate temperature control conditions have been maintained during transit for all study treatments received and confirm that any discrepancies are reported and resolved prior to study treatment administration.

The study treatment will be maintained in a monitored, environmentally controlled (in accordance with treatment labeling), secure, locked area with restricted access at the study site.

Only subjects enrolled in the study will receive study treatment and only authorized study staff will dispense study treatment.

In accordance with the International Council for Harmonisation (ICH) requirements, at all times the investigator will be able to account for all study treatment furnished to the study site. An accountability record will be maintained for this purpose. The investigator must maintain accurate records indicating dates and quantity of study treatment received, to whom it was administered (subject-by-subject accounting) and accounts of any study treatment accidentally or deliberately destroyed. All unused study treatment not involved in immediate subject treatment will be maintained under locked, temperature-controlled storage at the study site.

### **6.3. Measures to Minimize Bias**

This is an open-label study. Subjects will be randomized according to a pre-specified, validated computer-generated allocation scheme to receive the 4 treatments described above based on a 1:1:1:1 ratio.

Each subject will be assigned a unique identification (ID) number. The subject ID number will be assigned electronically by the INFORM database system when the study site staff enters the required information into the INFORM system. The subject ID number will be used to identify the subjects for the duration of the study within all systems and documentation. A subject with a signed ICF in place will be assigned a 4-digit sequential subject number preceded by the 4-digit study site number with a “dash” in between (ie, XXXX-XXXX). Each part must start with a non-zero number.

If the subject is not eligible to receive study treatment, or should discontinue from the study, the subject ID number will not be reassigned to another subject.

In the event that a subject repeats any evaluation during the screening window, they will not receive a new ID number. In addition, subjects who fail screening and are rescreened will not receive a new subject ID number. Qualified subjects who meet all of the eligibility criteria will be randomized into the study.

The investigator must maintain a subject master log linking the subject ID to the subject’s name. The investigator must follow all applicable privacy laws in order to protect a subject’s privacy and confidentiality. Information that could identify a subject will be masked on material received by the sponsor.

Subjects will be randomized according to a treatment allocation scheme that will be sent to each site. The treatment assigned will be recorded in the source documentation.

Based on the randomized treatment assignment, the investigator or investigator’s designee will dispense the study treatment tablets (MNK6106 or rifaximin) for each subject.

### **6.4. Study Treatment Compliance**

Treatment compliance will be determined by drug accountability and dosing information recorded in the eCRF.

---

## 6.5. Prior and Concomitant Therapy

Use of all relevant concomitant medications/therapies will be recorded in the subject's eCRF.

The start and stop date, dose, unit, frequency, route of administration, and indication for all prior (taken within the 30 days prior to the Screening Visit) and concomitant (taken from the Screening Visit through to the Final Visit) medications and nondrug therapies (eg, blood transfusions, oxygen supplementation, physical therapy, etc.) received will be recorded.

### 6.5.1. Prohibited Concomitant Therapies

The following treatments will not be permitted during the study (from Randomization through to the Final Visit):

- Current use of drugs that could potentially interfere with renal excretion of PAGN, such as corticosteroids, haloperidol, valproic acid probenecid, estrone sulfate, ibuprofen, cimetidine, or diclofenac. Use of L-ornithine L-aspartate is prohibited.
- Current use of drugs whose plasma concentration may be affected by MNK6106, such as alfentanil, cyclosporine, midazolam, quinidine, or cimetidine. Metformin use is permitted at low doses. Doses of metformin > 1,000 mg should be discussed with the medical monitor prior to enrollment.
- Current use of AMMONUL® (sodium benzoate with sodium PAA), BUPHENYL® (sodium phenylbutyrate), RAVICTI, or other medications containing sodium benzoate or sodium phenylbutyrate.
- Current use of rifaximin (except for subjects randomized to rifaximin), oral neomycin, oral vancomycin or any other oral or parenteral antibiotic that could potentially alter gut flora. There should be a 5-day washout period for rifaximin use prior to the first dose of study drug.
- Current use of repaglinide.
- Receipt of an investigational product or device, or participation in a drug research study within a period of 30 days (or 5 half-lives of the drug, whichever is longer) before the first dose of study treatment.
- Any investigational drug, device, or procedure administered as part of a research study.

Exceptions to these restrictions during the subject selection process must be approved by the investigator and sponsor and will be discussed on a case-by-case basis. Once the study has started, if a subject is unable to comply with the restrictions described above, their participation in the study will be re-evaluated by the investigator, again in consultation with the sponsor. The decision to continue a subject who has received a concomitant medication as directed by the investigator for the treatment of an AE will also be made mutually between the investigator and sponsor.

---

If any prohibited medication is taken during the study, all pertinent information will be recorded in source documents and the eCRF. The designated study medical monitor (MM) must be informed immediately so the sponsor may determine whether to continue the subject in the study.

#### **6.5.1.1. Sedatives**

Due to the importance of accurately measuring mental status during the treatment period of this study, sedation is an important potential confounder, and thus, sedatives should not be used during the study period. Sedatives such as benzodiazepines (eg, alprazolam, alcyon, midazolam, oxazepam, triazolam, lorazepam, estazolam, temazepam, diazepam, chlordiazepoxide, clonazepam, flurazepam, clorazepate) and sleep aids (eg, haloperidol, zolpidem, Midol PM®, Sominex®, trazodone [Desyre1®], Sleep-eze®), are not allowed during the treatment period through completion of the final visit and, if applicable, + 24 hours after final visit assessments.

Any psychoactive agents including strong analgesics, antidepressants, and/or anxiolytics should be avoided. Narcotic use should be avoided due to subject sensitivity to these agents. Any use of sedation must be consistent with standard medical therapy. If sedation is unavoidable, use drugs with a short half-life (eg, diprivan) as well as drugs that do not have synergistic effects with endogenous promoters of HE (eg, avoid benzodiazepines).

Mind-altering agents (such as barbiturates, opioids, or benzodiazepines) should be avoided during the treatment period through completion of the final visit and, if applicable, + 24 hours after final visit assessments.

